7.1.2 Temporary discontinuation

If a participant discontinues study medication, no restart will be allowed.

7.1.3 Criteria for study hold due to adverse events

In recognition of the advanced status of the development program for PSL, the following hold/stopping rules will apply to this study.

In the event that either or both of the following criteria are met a safety review will be immediately initiated:

- The occurrence of a serious, unexpected adverse reaction (ie, an SAE considered at least possibly related to the study medication) in 2 study participants, where those serious adverse reactions occur in the same body system.
- The occurrence of a severe nonserious adverse reaction (ie, severe nonserious AEs considered at least possibly related to the study medication) in 3 study participants, where those severe adverse reactions:
 - Occur in the same body system, and

- Lead to withdrawal of the affected participant

The safety review will be conducted by an internal, study-specific Safety Monitoring Committee comprising comprised of the Investigator and appropriate members of the UCB Study Team (such as Study Physician, Safety Physician, Clinical Project Manager, and Clinical Pharmacologist), as quickly as possible, to review the available data and determine whether it is appropriate to continue dosing at the next scheduled dosing point. This will take the form of a risk/benefit evaluation from the perspective of the individual study participants. In making this evaluation, account will be taken of the potential risks of sudden discontinuation of study medication, particularly in participants who may be taking higher dose levels, and whether or not a taper off tapering period, and its duration / speed, should be undertaken.

If the Safety Monitoring Committee cannot be convened before the next scheduled dosing point, the Investigator will make an independent evaluation as to whether it is appropriate to continue dosing pending the review.

The Safety Monitoring Committee will also decide whether it is appropriate to continue the study with or without dose adaptations, additional safety assessments, or other changes in design. If such changes are deemed necessary to protect the wellbeing of participants, further dosing in the study will be suspended while a substantial amendment is submitted to the Country(ies) Health Authority and Research Ethics Committee(s) and the study will not restart until that amendment has been approved.

Detailed procedures for reporting SAEs and other safety events which may meet study hold/stopping criteria are provided in Appendix 3 (Section 10.3).

7.2 Participant discontinuation/withdrawal from the study

Study participants are free to withdraw from the study at any time, without prejudice to their continued care.

A study participant may withdraw from the study at any time at his/her own request, or may be withdrawn at any time at the discretion of the Investigator for safety, behavioral, compliance, or administrative reasons.

If the study participant withdraws consent for disclosure of future information, the Sponsor may retain and continue to use any data collected before such a withdrawal of consent.

If a study participant withdraws from the study, he/she may request destruction of any samples taken and not tested, and the Investigator must document this in the site study records.

See the Schedule of Activities for data to be collected at the time of study discontinuation and follow up and for any further evaluations that need to be completed.

Study participants should be withdrawn from the study if any of the following events occur:

1. The study participant develops a clinically relevant medical condition (physical or psychiatric) that, in the opinion of the Investigator, jeopardizes or compromises the study participant's ability to participate in the study or makes it unsafe to continue.
2. Study participant is noncompliant with the study procedures or medications in the opinion of the Investigator.
3. Study participant takes prohibited concomitant medications as defined in this protocol.

4. Study participant withdraws his/her consent.
5. There is confirmation of a pregnancy during the study, as evidenced by a positive pregnancy test.
6. The Sponsor or a regulatory agency requests withdrawal of the participant.
7. Study participant has changes in the ECG that are regarded as clinically significant and/or that worsen over time. An ECG shows an absolute confirmed value for QTcB or QTcF ≥ 500 ms or ≥ 60 ms above Baseline.
8. Study participant develops second- or third-degree atrioventricular block or another clinically relevant change in ECG as determined by the Investigator.
9. Study participant has active suicidal ideation without a specific plan as indicated by a positive response ("Yes") to Question 4 of the "Since Last Visit" version of the C-SSRS. The study participant should be referred immediately to a mental healthcare professional and may be withdrawn from the study based upon the Investigator's judgment of the benefit/risk ratio of continuing the study participant in the study on PSL.
 - Study participant has active suicidal ideation with a specific plan as indicated by a positive response ("Yes") to Question 5 of the "Since Last Visit" version of the C-SSRS. The study participant should be referred immediately to a mental healthcare professional and must be withdrawn from the study.
10. Study participant is suspected of having a serious multiorgan hypersensitivity reaction. Serious suspected multiorgan hypersensitivity cases may be identified and reported to the Sponsor by the Investigator using the following algorithm:
 - An AE or laboratory value (as defined below) suggestive of internal organ involvement including but not limited to hepatitis, nephritis, pneumonitis, carditis, colitis, encephalitis, pancreatitis, myositis, arthritis, or hematologic system involvement combined with at least 1 of the following: fever, rash, lymphadenopathy, or eosinophilia.
 - Treatment-emergent abnormal laboratory value criteria suggestive of internal organ involvement or eosinophilia:
 - Eosinophils percentage $\geq 10\%$
 - Eosinophils absolute ≥ 0.5 G/L
 - Neutrophils absolute < 1.5 G/L
 - Platelets absolute ≤ 100 G/L

Withdrawn participants should follow the taper schedule if possible unless faster discontinuation is considered necessary in the medical judgement of the Investigator. Investigators should attempt to obtain information on study participants in the case of withdrawal.

For study participants considered as lost to follow up, the Investigator should make an effort (at least 1 phone call and 1 written message to the study participant), and document his/her effort (date and summary of the phone call and copy of the written message in the source documents), to complete the final evaluation. All results of these evaluations and observations, together with a

narrative description of the reason(s) for removing the study participant, must be recorded in the source documents. The eCRF must document the primary reason for withdrawal.

Investigators should contact the Medical Monitor, whenever possible, to discuss the withdrawal of a study participant in advance.

Study participants withdrawn will be replaced at the discretion of the Investigator and Sponsor.

7.3 Lost to follow up

A study participant will be considered lost to follow up if he or she repeatedly fails to return for scheduled visits and is unable to be contacted by the study site.

The following actions must be taken if a participant fails to return to the clinic for a required study visit:

- The site must attempt to contact the participant and reschedule the missed visit as soon as possible and counsel the participant on the importance of maintaining the assigned visit schedule and ascertain whether or not the study participant wishes to and/or should continue in the study.
- Before a study participant is deemed lost to follow up, the Investigator or designee must make every effort to regain contact with the study participant (at least 1 phone call and 1 written message to the study participant), and document his/her effort (date and summary of the phone call and copy of the written message in the source documents), to complete the final evaluation. All results of these evaluations and observations, together with a narrative description of the reason(s) for removing the study participant, must be recorded in the source documents. The eCRF must document the primary reason for withdrawal.

Should the study participant continue to be unreachable, he/she will be considered to have withdrawn from the study with a primary reason of lost to follow up documented in the eCRF.

8 STUDY ASSESSMENTS AND PROCEDURES

Study procedures and their timing are summarized in the Schedule of Activities (Section 1.3).

Protocol waivers or exemptions are not allowed.

Immediate safety concerns should be discussed with the Sponsor immediately upon occurrence or awareness to determine if the participant should continue or discontinue study treatment.

Adherence to the study design requirements, including those specified in the Schedule of Activities (Section 1.3), is essential and required for study conduct.

All screening evaluations must be completed and reviewed to confirm that potential study participants meet all eligibility criteria. The Investigator will maintain a screening log to record details of all study participants screened and to confirm eligibility or record reasons for screening failure, as applicable.

The maximum amount of blood collected from each study participant over the duration of the study, including any extra assessments that may be required, will not exceed 500mL per study participant. Repeat or unscheduled samples may be taken for safety reasons or for technical issues with the samples.

8.1 Efficacy assessments

Not applicable.

8.2 Safety assessments

The safety and tolerability of repeated doses of PSL when co-administered with single dose of ethanol or in the setting of stable concomitant therapy with CBD will be monitored by evaluation of AEs, vital signs (pulse rate, body temperature, respiratory rate, SBP, and DBP), 12-lead ECG parameters, psychiatric and mental status findings, physical examination findings, clinical laboratory test results, and suicidal risk monitoring. Planned time points for all safety assessments are provided in the Schedule of Activities (Section 1.3).

8.2.1 Physical examination

Physical examinations will be performed at Screening at the time points specified in Section 1.3.

A complete physical examination will be performed at Screening and will include, at a minimum, general appearance; ear, nose, and throat; eyes, hair, and skin; assessments of the Cardiovascular, Respiratory, Gastrointestinal, Neurological, Musculoskeletal, and Hepatic systems; and mental status. Height and weight will also be measured and recorded.

A brief physical examination will be performed at the time points specified in Section 1.3. A brief physical examination will include, at a minimum, assessments of general appearance, skin, lungs, cardiovascular system, and mental status.

Investigators should pay special attention to clinical signs related to previous serious illnesses.

Clinically relevant findings or worsening of previous findings will be recorded as AEs.

8.2.2 Vital signs

Body temperature, pulse rate, respiratory rate, and blood pressure will be assessed as outlined in the Schedule of Activities (see Section 1.3).

Temperature may be measured by either oral or aural route at the discretion of the site, but must be performed using the same method in any individual participant on all occasions.

Blood pressure measurements will be performed in both supine and standing positions for orthostatic measurement at Screening (supine BP after the participant has been lying down for 5 minutes, then standing BP after 1 minute and 3 minutes), and in a supine position for routine blood pressure measurements at all assessments. Blood pressure and pulse measurements will be assessed with a completely automated device. Manual techniques will be used only if an automated device is not available.

Blood pressure and pulse measurements should be preceded by at least 5 minutes of rest for the participant in a quiet setting without distractions (eg, television, cell phones).

Vital signs (to be taken before blood collection for laboratory tests) will consist of 1 pulse and 1 blood pressure measurement.

8.2.3 Electrocardiograms

Triplicate 12-lead ECG will be obtained as outlined in the Schedule of Activities (see Section 1.3) using an ECG machine that automatically calculates the heart rate and measures PR,

QRS, QT, and QTc intervals. Refer to Section 7 for QTc withdrawal criteria and any additional QTc readings that may be necessary.

All ECG recordings should be taken with the study participant resting in the supine position for at least for ≥ 5 minutes before the recording.

At each time point at which triplicate ECG are required, 3 individual ECG tracings should be obtained as closely as possible in succession, but no more than 2 minutes apart. The full set of triplicates should be completed in less than 4 minutes.

8.2.4 Clinical safety laboratory assessments

See Appendix 2 (Section 10.2) for the list of clinical laboratory tests to be performed and to the Schedule of Activities for the timing and frequency.

The Investigator must review the laboratory report, document this review, and record any clinically relevant changes occurring during the study in the AE section of the eCRF. The laboratory reports must be filed with the source documents. Clinically significant abnormal laboratory findings are laboratory findings that change considerably or their frequency or intensity increases more than expected as compared to the clinical profile known to the Investigator from the study participant's history or Screening Period.

All laboratory tests with values considered clinically significantly abnormal during participation in the study or at the Follow-up Visit of study medication should be repeated until the values return to normal or Baseline or are no longer considered clinically significant by the Investigator or medical monitor.

If such values do not return to normal or Baseline within a period of time judged reasonable by the Investigator, the etiology should be identified and the Sponsor notified.

All protocol-required laboratory assessments, as defined in Appendix 2 (Section 10.2), must be conducted in accordance with the laboratory manual or equivalent document and the Schedule of Activities.

If laboratory values from nonprotocol specified laboratory assessments performed at the institution's local laboratory require a change in participant management or are considered clinically significant by the Investigator (eg, SAE or AE or dose modification), then the results must be recorded in the eCRF.

8.2.5 Suicidal risk monitoring

Padsevonil is considered to be an AED. Suicidal ideation and behavior have been reported in patients treated with antiepileptic agents in several indications. A meta-analysis of randomized placebo-controlled studies of AEDs has also shown a small increased risk of suicidal ideation and behavior. The mechanism of this risk is not known and the available data do not exclude the possibility of an increased risk for PSL.

Suicidality will be assessed by trained study personnel using the C-SSRS (Columbia University Medical Center, 2008). This scale will be used for screening as well as to assess suicidal ideation and behavior that may occur during the study. At the Screening Visit, "Baseline/Screening" version of the C-SSRS will be completed. At all other visits, "Since Last Visit" version of the C-SSRS will be completed as indicated on the Schedule of Activities (Section 1.3).

Participants being treated with PSL should be monitored appropriately and observed closely for suicidal ideation and behavior or any other unusual changes in behavior. Families and caregivers of participants being treated with PSL should be instructed to monitor participants for the emergence of unusual changes in behavior, as well as the emergence of suicidal ideation and behavior, and to report such symptoms immediately to the study Investigator. Consideration should be given to discontinuing PSL in participants who experience signs of suicidal ideation or behavior.

8.2.6 Psychiatric and mental status

Psychiatric and mental status will be assessed at Baseline and scheduled visits as specified in Section 1.3.

The psychiatric and mental status of participating subjects will be closely monitored. Assessment of specific domains of psychiatric and cognitive symptoms will be performed by a staff member trained in the identification of psychiatric symptoms. The parameters that will be evaluated are Psychiatric symptoms, mental impairment and behavioral problem (as orientation, attention, memory, mood, calculus, behavior, and thinking or feeling). These parameters will be assessed as normal or abnormal and then determined whether clinically significant. If present and abnormal, psychiatric symptoms, mental impairment, and behavioral problems will be assessed as to whether they are clinically significant.

8.3 Adverse events

The definitions of an AE or SAE can be found in Appendix 3 (Section 10.3).

Adverse events will be reported by the participant (or, when appropriate, by a caregiver, surrogate, or the participant's legally authorized representative).

The Investigator and any designees are responsible for detecting, documenting, and recording events that meet the definition of an AE or SAE and remain responsible for following up AEs that are serious, considered related to the study treatment or study procedures, or that caused the participant to discontinue PSL or UP0071 (see Section 7).

8.3.1 Time period and frequency for collecting AE and SAE information

All AEs and SAEs will be collected from the signing of the ICF and at the time points specified in the Schedule of Activities (Section 1.3).

Medical occurrences that begin before the start of study treatment but after obtaining informed consent will be recorded on the Medical History/Current Medical Conditions section of the eCRF, not the AE section.

All SAEs will be recorded and reported to the Sponsor or designee within 24 hours, as indicated in Appendix 4. The Investigator will submit any updated SAE data to the Sponsor within 24 hours of it being available.

The Investigator is specifically requested to collect and report to UCB (or its representative) any SAEs (even if the Investigator is certain that they are in no way associated with the study medication), up to 30 days from the end of the study for each participant, and to also inform participants of the need to inform the Investigator of any SAE within this period. Serious AEs that the Investigator thinks may be associated with the study medication must be reported to UCB regardless of the time between the event and the end of the study.

The method of recording, evaluating, and assessing causality of AE and SAE and the procedures for completing and transmitting SAE reports are provided in Appendix 3 (Section 1.3).

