- A "reasonable possibility" of a relationship conveys that there are facts, evidence, and/or arguments to suggest a causal relationship, rather than a relationship cannot be ruled out.
- The Investigator will use clinical judgment to determine the relationship.
- Alternative causes, such as underlying disease(s), concomitant therapy, and other risk factors, as well as the temporal relationship of the event to study medication administration will be considered and investigated.
- The Investigator will also consult the Investigator's Brochure (IB) and/or Product Information, for marketed products, in his/her assessment.
- For each AE/SAE, the Investigator **must** document in the medical notes that he/she has reviewed the AE/SAE and has provided an assessment of causality.
- There may be situations in which an SAE has occurred and the Investigator has minimal information to include in the initial report to UCB. However, **it is very important that the Investigator always make an assessment of causality for every event before the initial transmission of the SAE data to UCB.**
- The Investigator may change his/her opinion of causality in light of follow-up information and send a SAE follow-up report with the updated causality assessment.
- The causality assessment is 1 of the criteria used when determining regulatory reporting requirements.

Follow up of AEs and SAEs

- The Investigator is obligated to perform or arrange for the conduct of supplemental measurements and/or evaluations as medically indicated or as requested by UCB to elucidate the nature and/or causality of the AE or SAE as fully as possible. This may include additional laboratory tests or investigations, histopathological examinations, or consultation with other health care professionals.
- An AE should be followed until it has resolved, has a stable sequelae, the Investigator determines that it is no longer clinically significant, or the participant is lost to follow up. This follow-up requirement applies to AEs, SAEs, and AEs of special interest.
- If a participant dies during participation in the study or during a recognized follow-up period, the Investigator will provide UCB with a copy of any postmortem findings including histopathology.
- New or updated information will be recorded in the originally completed eCRF.
- The Investigator will submit any updated SAE data to UCB within 24 hours of receipt of the information.

Reporting of SAEs

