SAE Reporting to UCB via an Electronic Data Collection Tool

- The primary mechanism for reporting an SAE to UCB will be the electronic data collection tool.
- If the electronic system is unavailable for more than 24 hours, then the site will use the paper SAE data collection tool (see next section).
- The site will enter the SAE data into the electronic system as soon as it becomes available.
- After the study is completed at a given site, the electronic data collection tool will be taken off-line to prevent the entry of new data or changes to existing data.
- If a site receives a report of a new SAE from a study participant or receives updated data on a previously reported SAE after the electronic data collection tool has been taken off-line, then the site can report this information on a paper SAE form (see next section) or to the UCB Study Physician by telephone.
- Contacts for SAE reporting can be found in [SERIOUS ADVERSE EVENT REPORTING](#).

SAE Reporting to UCB via Paper CRF

- Facsimile transmission of the SAE paper CRF is the preferred method to transmit this information to the UCB Study Physician.
- In rare circumstances and in the absence of facsimile equipment, notification by telephone is acceptable with a copy of the SAE data collection tool sent by overnight mail or courier service.
- Initial notification via telephone does not replace the need for the Investigator to complete and sign the SAE CRF pages within the designated reporting time frames.
- Contacts for SAE reporting can be found in [SERIOUS ADVERSE EVENT REPORTING](#).

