10.4 Appendix 4: Contraceptive guidance and collection of pregnancy information

10.4.1 Definitions

10.4.1.1 Woman of childbearing potential

A woman is considered fertile following menarche and until becoming postmenopausal unless permanently sterile (see below).

Women in the following categories **are not considered WOCBP**:

1. Premenarchal
2. Premenopausal female with 1 of the following:
 - Documented hysterectomy
 - Documented bilateral salpingectomy
 - Documented bilateral oophorectomy

Note: Documentation can come from the site personnel's review of the participant's medical records, medical examination, or medical history interview.

3. Postmenopausal female
 - A postmenopausal state is defined as no menses for 12 months without an alternative medical cause. A high follicle stimulating hormone (FSH) level in the postmenopausal range may be used to confirm a postmenopausal state in women not using hormonal contraception or hormonal replacement therapy (HRT). However, in the absence of 12 months of amenorrhea, a single FSH measurement is insufficient.
 - Females on HRT and whose menopausal status is in doubt will be required to use 1 of the nonestrogen hormonal highly effective contraception methods if they wish to continue their HRT during the study. Otherwise, they must discontinue HRT to allow confirmation of postmenopausal status before study enrollment.

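### The paper backup for SAE reports is triggered by an outage longer than the 24-hour reporting limit itself, so some outages leave no expressly provided written route in time

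*Protocol*

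**What the plan says.** **Time limit.** Protocol Section 8.3.1: "All SAEs will be recorded and reported to the Sponsor or designee within 24 hours, as indicated in Appendix 4". The sentence does not say what starts the 24 hours. For follow-up data the start is given, in Section 10.3.3: "The Investigator will submit any updated SAE data to UCB within 24 hours of receipt of the information".

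**Route.** Section 10.3.3: "The primary mechanism for reporting an SAE to UCB will be the electronic data collection tool". The backup follows: "If the electronic system is unavailable for more than 24 hours, then the site will use the paper SAE data collection tool". On recovery of the system: "The site will enter the SAE data into the electronic system as soon as it becomes available". Fax is the preferred way to send the paper form. Under the same paper heading, "In rare circumstances and in the absence of facsimile equipment, notification by telephone is acceptable", but a call does not release the Investigator from the duty to "complete and sign the SAE CRF pages within the designated reporting time frames". The only other use of paper is for reports that arrive after the electronic tool has been closed at the end of the study at the site.

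**Cross-references.** Section 8.3.1 sends the reader to Appendix 4, whose title is "Contraceptive guidance and collection of pregnancy information". Its last sentence names Appendix 3 but gives the number as Section 1.3, which is the Schedule of activities. Sections 7.1.3, 8.3 and 8.3.3 give Appendix 3 (Section 10.3). The SAP does not deal with reporting routes.

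**The concern.** A backup route is there to protect a deadline when the main route fails. Here its stated trigger is longer than the deadline it should protect. Section 10.3.3 gives no express written route for the first 24 hours of an outage, and it still holds the paper pages to the reporting time frames.

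What is at stake is the timeliness of the formal SAE report. Section 8.3.4 treats prompt notification of the sponsor as essential. Section 7.1.3 relies on the Appendix 3 procedures for events that may meet the criteria for a study hold. The wrong pointers in Section 8.3.1 do not delay a report by themselves, but they send a reader who wants the procedure to the wrong place.

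**Working it through.** The plan states no figure to reproduce. The check compares the two 24-hour clocks.

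**Inputs**
- Reporting limit: 24 h (Section 8.3.1).
- Start of the reporting clock: site awareness, set to hour 0. This is an assumption for initial reports. The deadline is then hour 24.
- Paper trigger: an outage of more than 24 h, counted from loss of the system (Section 10.3.3, read literally).
- Outage start *s* in hours (negative if before awareness) and duration *D* in hours. The documents give neither the frequency nor the length of outages, so both are varied.

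**Formulas**
- The electronic tool is usable again at *s* + *D*.
- Paper opens at *s* + 24, and only if *D* > 24.
- First usable route: *R* = max(0, the earlier of these two times).
- The report is forced late if *R* > 24, by *R* − 24 hours.

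**Results**

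| Outage start *s* | Duration *D* | Electronic back | Paper opens | First route *R* | Result |
|---|---|---|---|---|---|
| −12 | 36 | 24 | 12 | 12 | 12 h left |
| −1 | 36 | 35 | 23 | 23 | 1 h left |
| 0 | 36 | 36 | 24 | 24 | no time left |
| 6 | 12 | 18 | does not open | 18 | 6 h left |
| 12 | 12 | 24 | does not open | 24 | just on time |
| 18 | 12 | 30 | does not open | 30 | 6 h late |
| 6 | 36 | 42 | 30 | 30 | 6 h late |
| 23 | 36 | 59 | 47 | 47 | 23 h late |

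**General pattern**
- *s* ≤ 0 (outage already running at awareness): *R* is at most max(0, *s* + 24), which does not exceed 24. Lateness is not forced, but the margin shrinks to nothing as *s* approaches 0.
- *s* > 0, report not yet sent: lateness is forced exactly when *s* + *D* > 24. The delay is *s* + *D* − 24 if *D* ≤ 24, and *s* if *D* > 24. It is therefore at most *s*, and under 24 h.

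An hourly grid (*s* from −72 to 23, *D* from 1 to 199) agrees: no late case with *s* ≤ 0, no exception to the rule for *s* > 0, and a largest delay of 23 h.

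**With the wait removed.** If paper may be used whenever the electronic tool is down, a route is always open and no case is forced late.

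**The case against.** The strongest reply is that Section 10.3.3 calls the electronic tool the primary route, not the sole one, and says when paper becomes mandatory without forbidding it sooner. The telephone provision depends on the absence of fax equipment, not on the length of an outage, and the reporting time frames continue to bind. A site that reads all this together can turn to paper early and satisfy both rules. This stands: the text is not an outright contradiction. But it leaves the site to infer permission for early paper use from silence, next to a trigger that suggests waiting.

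Three stronger conclusions may tempt a reader. The documents do not support them.

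- *Any SAE that meets an outage is late by rule, so none can be on time.* The two clocks start at different moments. Outages that end before the deadline allow timely electronic entry, and outages already running at awareness do not force lateness. One could count the 24 hours from the moment the site discovers the fault, so that paper would never open before the deadline. But the text speaks of the system being unavailable, not of the site knowing it.
- *Two more twice-daily dosing points (24 h / 12 h = 2) pass before the sponsor knows.* This treats late form entry as an uninformed sponsor. Section 8 requires immediate discussion of immediate safety concerns with the sponsor, whatever the reporting tool. Under Section 7.1.3 the Investigator judges continued dosing alone if the safety committee cannot meet before the next dosing point. The study has one center.
- *The wrong appendix leaves the site without a procedure.* Section 8.3.1 itself names Appendix 3, and other sections cite it correctly.

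The SAE contact page to which Section 10.3.3 refers is not in the public text, so a further route given there cannot be excluded.

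**Conclusion.** The point holds in a limited form. The stated backup trigger (more than 24 h) is longer than the reporting limit (24 h). With the clock assumed to start at awareness and the trigger read literally, an outage that begins after awareness, before the report is sent, and lasts past hour 24 leaves no expressly provided written route in time. The forced delay is under 24 h. An outage that begins shortly before awareness can leave little or no time. How often this would happen cannot be estimated from the documents.

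The effect is on safety-reporting procedure only: no endpoint, sample size, randomization or analysis changes. The change is still worth making, because a stated rule can defeat a safety deadline and the remedy is a matter of wording. The two wrong references in Section 8.3.1 are clerical.

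**What to change.** 1. **Section 10.3.3.** Replace the condition of more than 24 hours with wording such as: *If the electronic system is unavailable when the report is to be made, the site will use the paper SAE form (fax or telephone) in time to meet the 24-hour limit and enter the data electronically later.*
2. **Section 8.3.1 (clerical).** Cite Appendix 3 (Section 10.3) in place of Appendix 4, and again in place of Appendix 3 (Section 1.3).

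Both are changes of wording. The downside is an occasional duplicate paper and electronic entry for the same event.
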